9.8.2. Derived and transformed data

Some of the data elements needed for the study objectives will be derived from available data during the analysis phase of the study. Details about these calculations are provided along with the operational definition in Table 1. Prior to constructing these variables, the Ontada biostatistician will perform data validation activities. Data validation will continue and will consist of, but is not limited to, quality control checks for appropriate values, logical sequences, and quantity of missing values.

Missing data will be identified and reported in the results tables as percentages for all variables. If there is a large amount of missing or illogical data, a decision to include, exclude or impute that variable will be subsequently made based on the study sponsor's decision.

9.8.3. Statistical methods

Description of study enrollment

To be included in the study patients must meet each of the inclusion criteria and none of the exclusion criteria listed in Section 9.3.1. Counts of patients excluded for each criterion will be summarized.

Additionally, the counts of patients to be classified into the following subgroups will be presented⁵:

- Cohort A: All alectinib treated patients (overall population)
- Cohort B (Alectinib only cohort): Alectinib treatment ongoing, or discontinued and no subsequent treatment⁶
- Cohort C: Alectinib followed by treatment X (top 3 most frequent)
- Cohort D: Alectinib followed by treatment Y (top 3 most frequent)
- Cohort E: Alectinib followed by treatment Z (top 3 most frequent)

Description of patient demographic, clinical and treatment characteristics

Descriptive analyses will be conducted to evaluate the demographic, clinical and treatment characteristics overall, as well as for each of the study cohorts. Results will be reported in

⁵ Final cohorts will be decided upon sample size. Patients receiving chemotherapy after initiating alectinib will be included in the patient sample

⁶ Patients with ongoing alectibin treatment, patients who discontinued alectinib and patients who did not have a subsequent treatment may be analyzed as separate cohorts depending on sample size of patients

aggregate. Categorical variables (e.g., ECOG performance status) will be reported as frequency and percentage. Continuous variables such as age will be reported as mean, standard deviation, median and range (minimum-maximum). In the case of missing observations, the number and percentage of missing values will be reported.

For comparative analysis, i.e. comparing 2 or more treatment groups (e.g., ALK inhibitor sequences) or strata (front-line alectinib and non front-line alectinib), statistical significance will be reported with level of statistical significance based on p = 0.05 level as well as 95% confidence intervals.

Chi-square testing will be used to assess associations between categorical variables when patient counts for single cells within the results tables are greater or equal to 5. When distribution cannot be assumed to be Chi-square, then Fisher's exact test will be used. Depending on normality, Analysis of variance (ANOVA)/t-tests or Kruskall-Wallis tests will be used for continuous variables. An alpha level of 0.05 will be the primary criterion for statistical significance of this study.

All descriptive tables will be presented for each of the study cohorts defined above and, as supported by the final sample size, stratified by front-line alectinib and non front-line alectinib treatment groups.

For Phase 3 exploratory objectives, descriptive analyses will be conducted to evaluate the demographic, clinical and treatment characteristics among patients treated with lorlatinib. Results will be reported in aggregate. Categorical variables (e.g., ECOG performance status) will be reported as frequency and percentage. Continuous variables such as age will be reported as mean, standard deviation, median and range (minimum-maximum). In the case of missing observations, the number and percentage of missing values will be reported.

Clinical outcomes

ALK inhibitor DOT, OS, PFS will be assessed using the Kaplan-Meier method with 95% CIs, and summary tables of the number of events and censored patients at 3, 6, 12, 18, and 24 months. Further details about these calculations are presented below and in Table 1.

Clinical outcome results will be presented by study cohort and stratified by front-line alectinib and non-front line alectinib (pending sample size).

Overall survival (OS) will be defined as the interval between start date of alectinib to the date of death as documented in the LADMF and/or iKM EHR database. Patients who did not die will be censored on the study end date or the last visit date available in the database, whichever occurred first. In order to handle censoring, the Kaplan-Meier method will be used to calculate median overall survival with 95% confidence intervals (in number of months). Additionally, 3, 6, 12, 18, and 24-month survival probabilities will be reported. OS will be estimated for the full study population and stratified by study cohort. Log-rank tests will be used to assess statistical differences.

Duration of Therapy (DOT) for ALK inhibitors: An intent to treat approach will be used. DOT will be defined as duration of time (in months) between alectinib treatment initiation and discontinuation, or the last administration date of alectinib, or start date of a subsequent ALK inhibitor, initiation of any subsequent non-ALK inhibitor treatment (as a proxy for evidence of discontinuation), death or check-in in a hospice will be used as a stop date.

There may be some patients who do not have evidence of discontinuation or who do not move on to a subsequent therapy.

Descriptive statistics (mean, median) and K-M methodology will be calculated from initiation of alectinib, until evidence of discontinuation for any reason, including but not limited to a treatment stop date, a last alectinib administration date, or evidence of new ALK inhibitor treatment or non-ALK inhibitor treatment. Patients who do not have evidence of discontinuing, starting new therapy, or whose last prescription date is <30 days from the end of the study period, will be censored at last visit date or end of study period.

$$DOT = (\frac{\textit{date of ALK treatment discontinuation - index date} + 1}{30.4375})$$

Progression-free survival: The PFS will be measured from the initiation of alectinib to the date of progression or date of death due to any cause, censoring patients who are still alive at the end of the study observation period and did not progress at the last visit date. Progression will be clinician-noted progression as noted per physician notes only, not by traditional Response Evaluation Criteria in Solid Tumors (RECIST) imaging, as this is impacted by frequency of imaging and may not be assessed the same across groups in daily clinical practice. Patients who did not progress or die will be censored on the study end date or the last visit date available in the database, whichever occurred first. The PFS will be estimated in months using the Kaplan-Meier method with 95% CIs, and summary tables of the number of events and censored patients at 3, 6, 12, 18, and 24 months. PFS will be estimated for the full study population and separately by study cohort. Log-rank tests will be used to explore statistical differences.

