Data Sources: Structured data fields within the iKM EHR database will provide information needed to address most research questions. These data will be supplemented by additional unstructured data collected through chart review for a subset of the study population.

Study size

A preliminary feasibility assessment for Phases 1 and 2 identified 293 patients who were treated with alectinib after 01 November 2017, with approximately half treated in the front-line setting. Approximately 20-30% of these patients received a subsequent therapy after alectinib. It is estimated that approximately 300 patients will be included in the Phase 1 structured data analysis. Targeted chart review for Phase 2 is proposed to occur on 150 patients receiving alectinib to identify at least 100 patients who received alectinib as front-line.

For Phase 3 structured analysis, a preliminary feasibility assessment identified 521 patients who were treated with alectinib from 01 June 2017 through 31 December 2020. Chart review for Phase 3 will include patients who had ongoing treatment at the end of Phase 2 study period, and an additional 125 patients will be targeted to identify 100 new patient who received alectinib as front-line therapy. For Phase 3 exploratory analysis, a preliminary feasibility assessment identified 134 patients who were treated with lorlatinib from 01 November 2018 through 31 December 2020.

The final study population for analysis will be defined after identification and review of the patient population meeting the eligibility criteria in the iKM database. A specific power calculation will not be performed as this is a descriptive analysis.

Data analysis

Descriptive analyses will be conducted to evaluate demographic, clinical and treatment characteristics overall, as well as for each of the study cohorts. Time-to-event outcomes (OS, DOT, PFS) will be assessed using the Kaplan-Meier method with 95% CIs and summary tables. All analyses will be presented for each of the study cohorts and, as supported by the final sample size, stratified by front-line alectinib and non front-line alectinib treatment groups.

Milestones

Interim reports for Phase 1 are expected to be delivered May 2020, with the final study report expected October 2020.

The final report for Phase 3 is expected to be delivered in March 2022.

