9.6. Study size

A preliminary feasibility assessment for Phases 1 and 2 identified 293 patients who were treated with alectinib after 01 November 2017, with approximately half treated in the front-line setting. Of the 293 patients receiving alectinib, 74% (n=217) patients had an ALK result. Approximately 20-30% of the 293 patients received a subsequent therapy after alectinib. It is estimated that approximately 300 patients will be included in the Phase 2 structured data analysis. Targeted chart review for Phase 2 is proposed to occur on 150 patients receiving alectinib to identify at least 100 patients who received alectinib as front-line. In the event the total number of eligible patients following structured data screening exceeds the planned number of charts for review, a random sample will be selected.

For Phase 3 structured analysis, a preliminary feasibility assessment identified 521 patients who were treated with alectinib from 01 June 1 2017 through 31 December 2020. Chart review for Phase 3 will include patients who had ongoing treatment at the end of Phase 2

study period, and an additional 125 patients will be targeted to identify 100 new patient who received alectinib as front-line therapy. For Phase 3 exploratory analysis, a preliminary feasibility assessment identified 134 patients who were treated with lorlatinib from 01 November 2018 through 31 December 31 2020.

The final study population for analysis will be defined after identification and review of the patient population meeting the eligibility criteria in the iKM database. A specific power calculation will not be performed as this is a descriptive analysis.

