9.8.1. Analysis sets

Phases 1 and 2

For analyses performed to meet the Phase 1 objectives, all patients who the meet the eligibility criteria defined in Section 9.3.1 will be considered. The study cohorts will be identified based on subsequent therapy following alectinib. For these analyses, datasets consisting of the structured data elements, plus the LADMF to confirm vitality status, required for the landscape analyses will be constructed.

The Phase 2 (chart review) analyses will be limited to a sample of 100 qualified front-line alectinib patient charts identified from Phase 1. The chart review analysis sets will be constructed from both structured and unstructured data, with the LADMF used to confirm vitality status.

Phase 3

For analyses performed to meet the Phase 3 unstructured objectives, all patients who the meet the eligibility criteria defined in Section 9.3.1 will be considered. The study cohorts will be identified based on subsequent therapy following alectinib. For these analyses, datasets consisting of the structured data elements, plus the LADMF to confirm vitality status, required for the landscape analyses will be constructed.

Phase 3 chart review analyses will include a subset of patients from Phase 2 chart review who had ongoing treatment at the end of the observation period and an additional sample of 100 qualified front-line alectinib patients from Phase 3. The chart review analysis sets will be constructed from both structured and unstructured data, with the LADMF used to confirm vitality status.

Some data elements will be captured with both structured and unstructured data. Since the chart review data are expected to provide a richer source of information, if data are available from both sources for a single patient, then chart review data will supersede what is available in the structured iKM data for the final analysis. To account for this, a final analysis data set will be constructed and used to update the landscape analyses once chart review data are available.

For Phase 3 exploratory analysis, all patients who meet the eligibility criteria defined in Section 9.3.2 will be considered. The study cohorts will be identified based on subsequent therapy following lorlatinib. For these analyses, datasets consisting of the structured data elements will be constructed.

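### Section 9.8.3 chooses between chi-square and Fisher's exact test on observed instead of expected cell counts, so for a small cohort against a large one the result can decide the test; the effect is small

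*Combined protocol and SAP*

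**What the plan says.** Section 9.8.3 sets out how categorical variables are compared between cohorts. Chi-square is used "when patient counts for single cells within the results tables are greater or equal to 5". The next sentence adds: "When distribution cannot be assumed to be Chi-square, then Fisher's exact test will be used". It gives no threshold of its own.

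The tests apply when "comparing 2 or more treatment groups (e.g., ALK inhibitor sequences) or strata (front-line alectinib and non front-line alectinib") are compared, and "An alpha level of 0.05 will be the primary criterion for statistical significance of this study". Whether p-values are one- or two-sided is not stated.

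The cohorts are the overall population (A), alectinib only (B) and the three most frequent next treatments (C, D, E). On size, the abstract says: "It is estimated that approximately 300 patients will be included in the Phase 1 structured data analysis". Section 9.6 says: "Approximately 20-30% of the 293 patients received a subsequent therapy after alectinib". Section 9.8.1 says: "The Phase 2 (chart review) analyses will be limited to a sample of 100 qualified front-line alectinib patient charts". Section 9.8 states that no separate SAP will be written, so no later document is planned that would refine the rule.

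**The concern.** The usual condition for Pearson's chi-square concerns expected counts. These are fixed by the table margins and do not depend on which way the difference goes. Observed counts do depend on it. If a small cohort shows an excess, its cell tends to reach 5 and the table gets chi-square. If it shows a deficit of the same size, the cell tends to fall below 5 and the table gets Fisher's test, which is usually more conservative. The choice of test then follows the result.

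At stake are borderline significance statements about the characteristics of Cohorts C to E. These cohorts are likely to be small, and they are set against a much larger alectinib-only group.

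**Working it through.** The documents contain no calculation behind this rule, so there is no figure to reproduce. The check compares two rules on 2x2 tables: the plan's (all observed cells at least 5) and the usual one (all expected cells at least 5). It uses Pearson chi-square without continuity correction and two-sided Fisher, both at 0.05.

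**Sizes.**
- Phase 1 scale: 300 patients, of whom 20-30% gives 60-90 with a next treatment. Assuming 25% and an even three-way split, each cohort has 300 x 0.25 / 3 = 25, and Cohort B has 300 - 75 = 225.
- Phase 3 scale: 521 patients in the feasibility count. If the 20-30% share is unchanged, 104-156 have a next treatment, or about 35-52 per cohort, and B has about 365-417. 40 v 390 represents this.
- 25 v 496 is one small cohort against everyone else (521 - 25 = 496).

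The shares, splits and true rates are assumptions; the documents give only the 20-30%.

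**Formulas.** For a table with cells a, b (small group, n1) and c, d (large group, n2), with m = a + c and N = n1 + n2:
- expected count for a = n1 x m / N
- X² = N(ad - bc)² / [n1 n2 m (N - m)]

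**Example 1, 7/25 v 63/496.** The expected count is 25 x 70 / 521 = 3.4 and the smallest observed cell is 7.
- ad - bc = 7 x 433 - 18 x 63 = 1897
- X² = 521 x 1897² / (25 x 496 x 70 x 451) = 4.79, p = 0.029
- Fisher p = 0.063

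The plan's rule takes chi-square; the expected-count rule takes Fisher. The verdict changes.

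**Example 2, 25 v 225, 60 with the characteristic.** The expected count is 25 x 60 / 250 = 6.0.
- 10/25 (four above): ad - bc = 10 x 175 - 15 x 50 = 1000
- 2/25 (four below): ad - bc = 2 x 167 - 23 x 58 = -1000
- For both, X² = 250 x 1000² / (25 x 225 x 60 x 190) = 3.90, p = 0.0483

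Under the plan, 10/25 gets chi-square (0.0483; Fisher would give 0.0803) and 2/25 gets Fisher (0.0503). Under the expected-count rule both get chi-square.

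**How often it matters.** The rejection probability is the sum over all (a, c) of Bin(a; n1, π1) x Bin(c; n2, π2), taken where p is at most 0.05. With equal rates, false positives (%) are:

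| Sizes, rate | Higher: plan / expected | Lower: plan / expected | Different test (% of tables) |
|---|---|---|---|
| 25 v 496, 10% | 3.7 / 2.8 | 0.02 / 0.02 | 9.8 |
| 25 v 496, 15% | 3.4 / 2.3 | 1.26 / 1.26 | 31.8 |
| 25 v 496, 20% | 3.3 / 2.8 | 1.41 / 1.43 | 43.4 |
| 25 v 225, 25% | 3.09 / 3.06 | 1.62 / 1.85 | 21.5 |

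(Higher and lower refer to the small cohort.)

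The significance verdict differs in far fewer tables than the test does: 0.5-1.1% in the 25 v 496 rows and 0.3% in the 25 v 225 row. At 40 v 390 it differs in 0.8% of tables at a 10% rate and 0.2% at 15-20%.

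**Power when the small cohort is truly lower, plan v expected-count rule.**
- 25 v 496, 5% v 25%: 69.0% v 74.1%
- 30 v 100, 8% v 30%: 70.6% v 76.0%
- 25 v 225, 5% v 25%: 69.5% v 70.9%
- 40 v 390, 5% v 25%: 93.3% v 93.6%

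**Equal groups.** At 25 v 25 both directions are treated alike. Total error at a 30% rate is 3.4% under the plan and 5.3% under the expected-count rule. At 40-50% it is 5.7-6.5% and 6.0-6.5%.

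**The case against.** The strongest reply is that the sentence beginning "When distribution cannot be assumed to be Chi-square" is a validity condition and can be read to cover low expected counts. On that reading Example 1 already goes to Fisher. This shows that the text is ambiguous, but it does not settle the matter. Expected counts appear nowhere in the documents, and the only threshold given refers to patient counts in the results tables. Nor does that sentence rescue 2/25 in Example 2, which fails the threshold although its expected count is 6.0.

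Several other points stand and limit the concern:
- Most of the lopsidedness is not caused by the rule. Pearson chi-square is itself asymmetric in unequal groups, and the lower tail is almost the same under both rules.
- The 5-point power losses need particular settings. 496 pools B with the other post-alectinib cohorts and matches no defined cohort. Against a group the size of B the loss is 1.5 points or less.
- Two-category tables for cohorts under 10 go to Fisher under either rule. That would be typical in Phase 2, where 20-30 patients split three ways leave about 7-10 each.
- The study is declared descriptive and has no power calculation.

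A reader might also infer that the rule inflates the overall false-positive rate. The enumeration does not support this. For a small cohort against a large one, total error under the plan stays below 5%. It exceeds 5% at 25 v 25 with rates of 40-50%, but the expected-count rule does no better there.

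**Conclusion.** The point holds as a minor one. The only working criterion in Section 9.8.3 uses observed counts, so for a small cohort against a much larger group the observed result can decide which test is applied. At the assumed sizes with equal true rates, this changes the significance verdict in about 1.1% of such tables at most. It raises false positives for an excess in the small cohort by up to about 1 percentage point, and it costs about 0.2 to 5 points of power to detect a deficit.

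The documents do not support two stronger readings. The first is that direction always determines the test: between equal-sized cohorts the choice follows the size of the difference, not its direction. The second is that the study's main outcomes are affected: duration of therapy, OS and PFS use Kaplan-Meier estimates, with log-rank tests for OS and PFS, and are untouched.

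The figures rest on two-category tables, two-sided tests, uncorrected chi-square and the assumed cohort sizes and rates.

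**What to change.** Replace the two sentences in Section 9.8.3 with one rule: chi-square test when all expected cell counts are at least 5; otherwise Fisher's exact test. State there that p-values are two-sided, if that is meant.

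The cost is a few words. No new data are needed, and expected counts follow from the table margins. The change makes the choice of test independent of direction. It does not remove the asymmetry of chi-square in unequal groups, nor does it guarantee an error rate below 5% in small equal groups.

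Using Fisher's test for every small-cohort comparison would also stop the result from choosing the test, but it would not recover the lost power: 69.0% and 70.4% in the first two power settings above, against 69.0% and 70.6% under the plan.

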Overall survival (OS) (alectinib and stratified by subsequent treatment)	iKM structured data + LADMF + chart review (derived)	Clinical outcomes	Study observation period	OS will be defined as the interval (in months) between alectinib start date and the date of death (any cause) as documented in the LADMF and the iKM EHR database. OS will be reported for overall alectinib and stratified by subsequent treatment. Patients who did not die within the study observation period will be censored on the study end date or the last visit date available in the dataset, whichever occurred first. OS will be analyzed using the Kaplan-Meier method with 95% CIs, and summary tables of the number of events and censored patients 3, 6, 12, 18, and 24 months.
Progression date after index date (physician- assessed)	Chart review	Clinical outcomes	Study observation period	Physician-assessed disease progression (and corresponding date of note) recorded from physician's progress notes in Chart Review.
Progression- free survival (alectinib, and subsequent treatment)	iKM structured data + LADMF + chart review (derived)	Clinical outcomes	Study observation period	The PFS will be measured from the initiation of alectinib to the date of progression or date of death due to any cause, censoring patients who are still alive at the end of the study observation period and did not progress at the last visit date. PFS will be reported for overall alectinib and stratified by subsequent treatment. The PFS will be estimated in weeks using the Kaplan-Meier method with 95% CIs, and summary tables of the number of events and censored patients at 3, 6, 12, 18, and 24 months.

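### OS and PFS are timed only from alectinib start, so the post-alectinib outcomes in Objectives 4, 9 and 10 are not estimated as written, and cohort log-rank tests compare groups formed after time zero

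*Combined protocol and SAP*

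**What the plan says.** Section 8 sets Objective 4, without condition, as overall survival after alectinib by subsequent treatment. Objectives 9 and 10 ask for PFS and OS in the same terms, if the final sample size supports them.

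Section 9.8.3 gives one clock for OS: "Overall survival (OS) will be defined as the interval between start date of alectinib to the date of death as documented in the LADMF" and/or the EHR. It continues: "OS will be estimated for the full study population and stratified by study cohort. Log-rank tests will be used to assess statistical differences". For PFS: "The PFS will be measured from the initiation of alectinib to the date of progression or date of death due to any cause", and then: "PFS will be estimated for the full study population and separately by study cohort. Log-rank tests will be used to explore statistical differences". Table 1 (Section 9.4) repeats the alectinib-start clock for both endpoints and adds for OS: "OS will be reported for overall alectinib and stratified by subsequent treatment".

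Sections 9.8.1 and 9.8.3 form the cohorts from therapy received after alectinib. A is everyone, B has no subsequent treatment (ongoing or discontinued), and C, D and E are the three most frequent next treatments. Section 9.8.3 sets a 0.05 criterion for "comparing 2 or more treatment groups (e.g., ALK inhibitor sequences) or strata".

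Index date-2, the start of the next treatment, is defined in the Abstract, Section 9.3 and Table 1. No OS or PFS definition refers to it. Section 9.8 says that no further SAP will be written.

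**The concern.** There are two linked problems.

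- **Wrong quantity.** Survival after the next treatment starts is a different quantity from survival after alectinib starts. If the plan is followed exactly, the curves labelled by subsequent treatment will show time since alectinib start, and nothing will answer Objectives 4, 9 and 10.
- **Groups formed after time zero.** A patient enters C, D or E only by living long enough to start another treatment. Cohort B holds patients who died before any switch together with patients still on alectinib. A log-rank test from alectinib start that sets B against C to E therefore partly measures how the cohorts were built.

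At stake are one unconditional objective, two conditional ones, and p-values at the 0.05 level that could be read as differences between treatment sequences.

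**Working it through.** The plan states no power, event count or effect size for OS or PFS, so there is no figure of its own to reproduce. The main check is textual; the simulations only illustrate it.

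**1. Objectives against definitions**

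| Objective | Asked for | Clock in 9.8.3 and Table 1 | Clock needed |
|---|---|---|---|
| 4 | Post-alectinib OS by next treatment | Alectinib start | Index date-2 |
| 9 (if sample size allows) | Post-alectinib PFS by next treatment | Alectinib start | Index date-2 |
| 10 (if sample size allows) | Post-alectinib OS by next treatment | Alectinib start | Index date-2 |

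**2. PFS.** Let P be the time from alectinib start to progression and S the time to the next treatment. PFS time is min(P, death). Where switching follows progression, P ≤ S, so the event in C to E is progression on alectinib and occurs before the next treatment begins.

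**3. Null simulations for OS** (next treatment has no effect on death). Inputs:
- N=300 (Abstract): 25 months of identification, data cut at month 31.
- N=473 for Phase 3: the 521 patients of Section 9.6 span 43 months (June 2017 to December 2020) and identification lasts 39, so 521 × 39/43 = 473. Data cut at month 51.
- 30% switching, the upper end of the 20-30% in Section 9.6.
- Assumed: exponential death and switch times, switching independent of death, administrative censoring only, and median OS of 24 to 81.6 months. The upper value is 6.8 years × 12 from Section 7, which runs from stage IV diagnosis.

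| Log-rank test (nominal 5%) | Null rejection |
|---|---|
| B v C-E pooled, from alectinib start | 54-100% |
| B v C v D v E, from alectinib start | 29-100% |
| C v D v E, from alectinib start, four-fold spread in switch hazards | 3-8% |
| C v D v E, from alectinib start, lorlatinib only from month 17 | 6-16% |
| C v D v E, from index date-2 | 3-6% |

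Example: with N=300, median OS 48 months and about 30% switching, mean 12-month OS is 0.80 in B and 0.94 in C to E. The truth for everyone is 2^(-12/48) = 0.84.

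The lorlatinib row uses Section 7: brigatinib was approved in April 2017 and lorlatinib in November 2018, 17 months after identification opens in June 2017. It assumes that lorlatinib takes 65% of switches after approval.

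**4. Sign of the B contrast.** Now let switching follow progression (N=473, 20-30% switching). Half the patients have median PFS 25.7 months (Section 7) and half an assumed 10-15 months. B versus pooled switchers, by assumed median months to death before/after progression:
- 60/40: HR 0.60-0.67, rejection 50-81%, favouring switchers.
- 100/12: HR 1.34-1.59, rejection 50-90%, against switchers.
- 100/40 and 100/24: rejection 7-12%, little inflation.

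**5. Loss to follow-up.** The plan censors at last visit. In a separate run with independent switching, an assumed 24-month median time to loss lowered four-group rejection from 15-88% to 2-66% (N=300) and from 62-100% to 23-93% (N=473).

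**6. Precision from index date-2.** The 95% half-width at a 50% estimate is 1.96 × 0.5/√n, ignoring censoring, with an equal three-way split:
- N=300: 300 × 20-30% / 3 = 20-30 per cohort, 18-22 points.
- N=473: 32-47 per cohort, 14-17 points.
- Front-line charts: 473 × 1/2 × 20-30% = 47-71 switchers, 16-24 per cohort, 20-25 points.

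**The case against.** The strongest reply is that the plan is incomplete rather than wrong. The Table 1 label for PFS mentions subsequent treatment, the DOT formula subtracts an unspecified index date, and index date-2 exists for patients who receive a next treatment. These show that a second clock may have been intended. They do not define one: the text under the PFS label starts at alectinib, and no later SAP will supply the rest. Nor can post-alectinib be read as after alectinib begins, since Table 1 uses the term for treatments received after alectinib.

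A second reply is that the study is descriptive. Section 9.6 gives no power calculation, Section 9.10.1 claims only associations, and PFS tests are exploratory. That limits the harm from the p-values, but a descriptive curve with the wrong origin still does not describe the stated objective.

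Three stronger readings are tempting and are not supported:
- **That a B versus C-E test is planned.** The text names no pairs. Cohort A contains all the others, so some selection is implied, and the example of ALK inhibitor sequences fits C, D and E at least as well.
- **That C versus D versus E from alectinib start is invalid unless switch timing is equal.** Rejection stayed near nominal with unequal timing. Delayed availability of lorlatinib raised it only modestly, by an amount that depends on an assumed share. OS from alectinib start by sequence is a legitimate descriptive quantity; it is not the one in Objective 4.
- **That Phase 3 chart review will add 100 switchers.** The groups listed in Section 9.3.4.2 include alectinib only.

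**Conclusion.** Wrong as written. Following the protocol exactly leaves Objective 4 unestimated, and Objectives 9 and 10 too if sample size allows. This rests on the text alone. In the structured data, Cohort A and the front-line/non-front-line strata keep a proper origin and are not affected.

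Any log-rank test that includes Cohort B against C to E would be invalid. A reader might infer from the high rejection rates that this study would falsely favour switchers. The documents do not support that: the rates are assumption-driven, fall with loss to follow-up, and can reverse or nearly vanish when switching follows progression. The size and sign of that bias are unknown.

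The distortion of C versus D versus E from alectinib start is modest: about 6-16% against a nominal 5%, assuming a 65% lorlatinib share after approval and switching independent of death.

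**What to change.** In Section 9.8.3 and Table 1:

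1. Add OS and PFS from index date-2 for Cohorts C to E, counting only progression or death after that date, as the analyses for Objectives 4, 9 and 10. Run log-rank tests by subsequent treatment only among C, D and E from that origin.
2. Keep alectinib start as the origin for Cohort A and the line-of-therapy strata. Show any Cohort B or C-E curves from alectinib start descriptively, without a test, and note that membership depends on later events.
3. Use one definition of index date-2. Table 1 and the Abstract (for Phase 3) limit it to next treatments in the identification period; Section 9.3 uses the observation period.
4. For PFS, confirm that chart review captures progression after index date-2. Table 1 lists "disease progression (and corresponding date of note) recorded from" physician notes but does not say which index date applies.

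**Cost.** OS needs only wording and code, because next-treatment start dates and death dates are already collected. For PFS, the planned discontinuation reason and end date of subsequent treatment give part of the information; progression without discontinuation may need its own field. Phase 3 re-reviews only Phase 2 patients with ongoing treatment at 31 December 2019, so some other Phase 2 charts might have to be reopened if that field was not captured. The price is shorter follow-up, no p-value against Cohort B, and the wide intervals shown above.
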